#### **12.8.4                   Definition of UPIRSOs, AE, and SAE.**

An unanticipated problem involving risks to subjects or others (UPIRSOs) is any experience or outcome that is unexpected, related or possibly related to the subject's participation in the study, and suggests that the research study places subjects or others at a greater risk of harm related to study procedures than was previously known or recognized. An Adverse Event (AE) is defined as any untoward medical occurrence experienced by a study subject participating in a clinical trial that may not have a causal relationship with the trial intervention. Any unwanted physical, psychological or behavioral change experienced by a study subject during their participation in the trial is considered an adverse event. For the purposes of this study, a Serious Adverse Event (SAE) is defined as an adverse event that results in death, is life threatening, requires hospitalization or prolongs an existing hospitalization, results in persistent or significant disability, or requires intervention to prevent one of the previously listed outcomes.

#### **12.8.5                   Documentation and Reporting.**

UPIRSOs, AEs and SAEs are documented and reported as per institutional protocol and IRB requirements. Research staff will identify any UPIRSOs or AEs and evaluate the severity, seriousness, study relatedness/expectedness, outcome and the need for change or discontinuation of the study intervention. All UPIRSOs must be reported to the MUSC IRB and include a description of the event, the date of occurrence, whether it is a local or outside report, how the event affected the rights, safety or welfare of the subject or others, current status of MUSC subjects, and any planned changes or modifications to the project as a result of the event. AEs are documented on AE logs and AE Case Report Forms. UPIRSOs and AEs must be reported to the IRB as soon as possible, but no later than 10 working days after the event or notification to the investigator that the event has occurred. Additional relevant information for UPIRSOs and AEs should be documented in a progress note in the research record to allow for monitoring and evaluation. All UPIRSOs, AEs and SAEs will be followed by research staff until resolution, stabilization or until the subject is no longer in the study.

The MUSC IRB requirements for reporting AEs includes all deaths that occur during the study or within 30 days of study termination regardless if they are expected or unrelated. Other AEs reportable to the MUSC IRB are those that are unexpected AND related or possibly related AND serious or more prevalent than expected. Unanticipated problems that do not meet the definition of an AEs require reporting to the IRB when there are: unexpected changes to the risk/benefit ratio of the research based on new findings, confidentiality breaches, participant or family member complaints, laboratory or medication errors, changes in FDA labeling or withdrawal from marketing of a drug or device, disqualification/suspension of investigators, unintentional changes to the IRB-approved protocol that may involve risks, deviation from the IRB protocol taken without prior IRB review to address apparent immediate hazard to a subject, and any deviation from the IRB-approved protocol that may increase risk or affects the participants rights, safety or welfare. The IRB meets monthly and communication with the IRB can occur via email, memos, official IRB forms and online reporting.

If an AE meets the definition of a SAE, appropriate SAE specific reporting forms are completed. Reportable SAEs must be reported to the MUSC IRB within 24 hours with AE

forms completed in conjunction with the PI. A report will also be sent to the NIH program officer assigned to the project. If complete information is not available within the 24 hour timeframe, follow-up information will be gathered to allow a complete evaluation of the event and outcome and will be forwarded to the NIH program officer as appropriate within 2 weeks. The PI will also provide a signed and dated SAE summary report.

## 13 Withdrawal from study

If for any reason a subject does not complete the study, the reason will be entered on the CRF. All subjects are free to withdraw from participation at any time, for any reason, specified or unspecified, and without prejudice. The Investigator must record the reason for the early termination.

## 14 STATISTICAL AND ANALYTICAL PLANS

Data analysis will be performed by the [name].

### 14.1 Sample Size Determination

Focus of this project lies on demonstration of feasibility (recruitment, retention and adherence rates) and usability (frequency, duration of app use; satisfaction/usability surveys-SUS, TSUQ, uMARS) rather than hypothesis-testing. Thus, sample size was determined for pragmatic reasons such as assessment of recruitment, drop-out and adherence rates. For categorical feasibility measures, with 50 SPs (25 per group), we will be able to estimate proportions with precision  $\pm 0.08$  to  $\pm 0.13$  for true population proportion (p) values for each outcome ranging from 0.10 to 0.30 (or correspondingly, from 0.70 to 0.90). For continuous usability measures, 95% confidence intervals (CIs) can be estimated with precisions ranging from  $\pm 0.20$  to  $\pm 0.78$  corresponding to estimated standard deviations (SDs) ranging from 0.5 to 2.0, respectively. For continuous impact measures (PSS,FAS, & QoL, FSE & TSRQ change scores), in intent-to-treat analyses, 95% CI estimates of within-group change scores (pre- to post-treatment) will have precisions ranging from  $\pm 0.1.5$  to  $\pm 2.4$  corresponding to estimated SD of change scores ranging from 3.7 to 6.1, respectively; between-group change scores differences will have precision estimates from  $\pm 2.8$  to  $\pm 3.7$  for SDs of differences in scores from 5.0 to 6.7 SD units.

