## SPARC

treatment satisfaction ( $\geq 75\%$  of sample will score above average on SUS(>68), uMARS (>64), TSUQ (>60)).

**Secondary outcomes:** Differences between the SPARC & SC groups in changes in fatigue (SAF), fatigue self-efficacy (FSE), stress (PSS), autonomous motivation (TSRQ) and QoL (KSQ). Any negative effect of SPARC on patients QOL will be recorded as part of the secondary outcomes.

**Procedures:** Consent will be obtained either on paper or eConsent will be obtained using Redcap. Following informed consent, SPs will be randomly assigned to SPARC or enhanced standard of care (SC) control group using the randomization module of the web-based REDCap study database. Standard of care includes education on stress and sarcoidosis fatigue, as well as recommending referral to pulmonary rehabilitation. Those in SPARC group will have SPARC app downloaded on their phone by the research coordinator. Use of the App will be reviewed and the subject will demonstrate ability to navigate the app, use components without assistance prior to leaving clinic. The research coordinator will assist in ensuring the SP have performed the first SPARC BAM session properly and completed the appropriate questionnaires prior to leaving the clinic.

A review of concomitant medications will be collected at the screening visit and reviewed at all study visits for changes. There are no patient-safety related adverse events possible, but any negative effect of SPARC on patients QOL will be recorded as part of the secondary outcomes. All SPs will return to clinic at weeks 4, 12 and 24 for routine clinical care. During those visits, questionnaires will be given, according to the Schedule of Assessments (Table 1-2). Questionnaires will be given orally or read on their own, based on their preference.

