**SPARC App Use:** SPs who randomize into the SPARC group will engage in BAM sessions for 10 min twice daily. The SPARC app is developed based on reviews of the SAF literature, and adaptation of the original TT app using SP & healthcare provider input with low literacy-based strategies and guided by the principles of Self-Determination Theory (SDT). SDT focuses on developing competence (akin to self-efficacy in Social Cognitive Theory) and autonomous regulation. Consistent strong effects of these SDT mediators have been observed for various health behavior changes (e.g., physical activity, smoking cessation, diet). We will promote autonomous motivation by sending tailored motivational/social reinforcement messages linking subjects' behavioral changes (e.g., adherence to BID BAM sessions) to their personal values, beliefs and short/long term goals derived from a branch logic questionnaire (Values, Beliefs, Goals Questionnaire). Domains identified include family, faith, friendships, community activities-membership/volunteer work; attendance and/or participation in leisure, sports & recreational activities and work related events. Domains frequently reported by subjects to be important drivers of behavior were "family, faith and friends." For example, God was often linked to having guided them to a "good doctor" or "pills that work and don't make me as tired." Power of prayer was often noted in conjunction with "praising God and showing thanks for the continued gift of life by treating my body as his temple." Family and community cohesiveness and support, especially activities with friends and family members were primary adherence motivators related to short-term life goals (e.g., increased time gardening, fishing, playing with grandchildren, attending church functions, etc.). Responses will guide delivery of >900 different automated motivational/social encouragement messages based upon levels of adherence to their SPARC regimen. A sample SMS feedback for an adherence score of 1.00 is: "*Way to go! Every day of Taming your tension keeps you on track for (patient identified values, e.g., "many more years watching those grandkids grow up").* If partially or completely non-adherent, he/she might receive: "*You must have been really busy yesterday. Get back on track with Tamer to keep reducing stress & fatigue and plan some special time with your grandkids.*"

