**SPARC**

With each use subjects place their finger over the phone's camera, which serves as a plethysmograph to collect the subject's real-time heart rate in response to deep breathing meditation. Compliance with the SPARC Meditation module use will be monitored based on heart rate data collected during a subject's use of the App. Viewing the heart rate graph also serves as a form of positive feedback for subjects. App usage analytics will assess SPARC App uptake (total engagement time) and its features (e.g., frequency of provider service line use, video modules: sarcoidosis & stress educational modules, BAM demo, SP testimonials, etc.).

Subjects will be provided \$50 compensation for time and effort at each evaluation. The App will have 2 links to address any issues with the app or their clinical care. Clinical care questions will be routed to the sarcoidosis nurse coordinator. Technical questions will be routed to the TACHL tech service line.

**Measures:** **Table 2** presents all outcome variables, questionnaires and timing of administration. Most scales have been used with 21-59 yr old AAs and Non-Hispanic Whites and have established psychometrics. We provide brief psychometric information (e.g., internal consistency, test-retest reliability).

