### 14.2 Data Analysis

Descriptive statistics will be calculated for all measures and variables. We will use 95% CIs for proportions to estimate dichotomous feasibility outcomes (e.g., proportion who agree to participate out of total approached, proportion adherent to SPARC protocol, and proportion who drop out). Frequency distributions will be developed describing participants' reasons for non-adherence and discontinuation of SPARC app use and problems/issues encountered with the app. For continuous usability measures (e.g., frequency, duration of use; surveys-SUS,TSUQ,uMARS), frequency distributions & median and mean responses (with 95% CIs) will be obtained. Mean change and difference in change between the groups from pre-to-post intervention along with their 95% CIs will be reported for all continuous secondary (impact) outcomes (change in PSS-10, FAS, QoL, FSE & TSRQ scores). Preliminary analyses will

SPARC

examine a) underlying distributional properties of all outcome variables b) patterns of missing data, and c) patterns of attrition. Linear mixed-models for repeated measures will be used for the continuous impact measures to obtain estimates of intra-cluster correlation (ICC) & variance estimates along with covariance structure of longitudinal scores used as critical information for sample size calculation of a future efficacy RCT. Based upon Shieh's work, we have inadequate sample size & lack of adequate power to run formal moderator analyses. These analyses will be run in the future appropriately powered RCT to examine impact of socio-demographic variables as potential adherence barriers, as well as potential moderating effects of disease severity (i.e. lung function), fatigue-inducing medications and SPARC meditation adherence on secondary outcomes

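### The ±0.08 to ±0.13 precision in section 14.1 needs 50 subjects, but only the 25 app users can be adherent: for the proportion adherent it is ±0.12 to ±0.18

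*Combined protocol and SAP*

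**What the plan says.** Section 14.1 opens with "Focus of this project lies on demonstration of feasibility (recruitment, retention and adherence rates) and usability" and explains that "sample size was determined for pragmatic reasons such as assessment of recruitment, drop-out and adherence rates". It then gives one statement for all categorical feasibility measures: "with 50 SPs (25 per group), we will be able to estimate proportions with precision" of ±0.08 to ±0.13, for true proportions between 0.10 and 0.30 or, by symmetry, between 0.70 and 0.90. The range is offered for each such outcome, with no separate figure for measures that exist in one arm only.

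Section 14.2 lists the dichotomous feasibility outcomes that will get 95% confidence intervals: "proportion who agree to participate out of total approached", together with "proportion adherent to SPARC protocol, and proportion who drop out".

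Section 9.1.3 shows who can contribute adherence data:

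- "Those in SPARC group will have SPARC app downloaded on their phone by the research coordinator".
- "SPs who randomize into the SPARC group will engage in BAM sessions for 10 min twice daily".
- "Compliance with the SPARC Meditation module use will be monitored based on heart rate data", and those data are collected while the subject uses the app.

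Under section 9.1 the control group receives education and the offer of a rehabilitation referral, with no app and no meditation sessions.

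**The concern.** A control subject has no sessions to adhere to and no app to record them, so the denominator for the proportion adherent is 25. A precision computed on 50 is too narrow by a factor of √2.

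Adherence is one of the primary benchmarks (section 8), and 14.1 cites it as a reason for the sample size. The trial is justified by precision rather than by power, so the precision statement is the whole of the quantitative case for 50 subjects. A reader would expect an interval of about ±0.13 around a 70% adherent share and would get about ±0.18. That matters when someone has to judge whether a result near the benchmark supports going on to a larger trial.

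**Working it through.** **Inputs.** 50 subjects, 25 per group (14.1). 95% intervals (14.2), so z = 1.96. True proportions 0.10 to 0.30, or 0.70 to 0.90 (14.1). Adherence possible in the SPARC arm only (9.1, 9.1.3).

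**Formula.** Wald half-width = 1.96 × √(p(1 − p)/n).

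**Step 1: the plan's own figure, n = 50.**

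- p = 0.10: 1.96 × √(0.09/50) = 0.083
- p = 0.30: 1.96 × √(0.21/50) = 0.127

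This reproduces ±0.08 to ±0.13. No n = 25 alternative that was tried does so: Wilson gives 0.122 to 0.169, Clopper-Pearson 0.135 to 0.190, and a 90% Wald interval 0.099 to 0.151.

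**Step 2: the same formula with the SPARC arm, n = 25.**

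- p = 0.10 (0.90): 1.96 × √(0.09/25) = 0.118
- p = 0.30 (0.70): 1.96 × √(0.21/25) = 0.180

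The ratio to step 1 is √(50/25) = 1.41.

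**Step 3: cross-check within 14.1.** The continuous usability precision, ±0.20 to ±0.78 for SDs of 0.5 to 2.0, reproduces at n = 25 (1.96 × 0.5/5 = 0.196; 1.96 × 2.0/5 = 0.784). At n = 50 it would be 0.139 to 0.554. The same paragraph therefore already uses one arm for app-related scores, but not for adherence.

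**Step 4: what the stated precision would require.** For ±0.13 at p = 0.70: n = 1.96² × 0.21/0.13² = 47.7, so about 48 app users.

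**Step 5: effect of drop-out.** If drop-outs count as non-adherent, n stays at 25. If they are excluded, attrition like the 5.5% in the proof-of-concept trial leaves about 24, giving ±0.18 at p = 0.70. A 20% loss leaves 20, giving ±0.13 to ±0.20.

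**Step 6: an example.** With 18 of 25 adherent (72%), the Wilson 95% interval is 52% to 86%, and the Clopper-Pearson interval is 51% to 88%.

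**Step 7: the other binary benchmarks.**

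| Outcome | Denominator | Half-width |
|---|---|---|
| Retention, p = 0.80 | 50 | 1.96 × √(0.16/50) = 0.111 |
| Recruitment, p = 0.80 | number approached, 50/0.80 = 62.5, about 63 | 1.96 × √(0.16/63) = 0.099 |
| Above-average SUS, uMARS or TSUQ, p = 0.75 | 25, if app users only | 1.96 × √(0.1875/25) = 0.170 |
| Same, 20% lost | 20 | 1.96 × √(0.1875/20) = 0.190 |

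Retention and recruitment fall inside the stated range, although the recruitment denominator is not 50. Section 14.1 gives no precision for the usability proportions, only for the continuous scores.

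**The case against.** The strongest objection is that the .70 benchmark may not be a share of subjects at all. Table 2 describes adherence as a percentage of the meditation dose, the proof-of-concept results are monthly percentages, and the app assigns each subject an adherence score. On that reading the quantity is a mean session rate and its precision depends on an SD. The documents give none; assuming 0.20 to 0.35, the half-width at n = 25 is 2.064 × SD/5 = 0.083 to 0.144, close to the stated range.

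Part of this stands. The contrast of ±0.18 with ±0.13 at 0.70 applies only to a share of subjects, and no section says what makes a subject adherent. But 14.2 names a proportion adherent, and it is for proportions that 14.1 gives its range. If the measure is a mean rate, a p(1 − p) precision does not apply, and the similarity of the numbers is coincidence. On neither reading does 14.1 give a correctly derived precision for adherence.

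It can also be said that sections 7 and 9.1.3 place adherence under usability. Sections 14.1 and 14.2 place it under feasibility, and the precision statement is theirs.

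Finally, this is a feasibility trial of pragmatic size, with no decision rule tied to interval width. That is true and limits the consequence, but it does not make the figure right.

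**Conclusion.** The concern holds. For the proportion adherent, the precision with 25 app users is ±0.12 to ±0.18, not ±0.08 to ±0.13, an understatement of the half-width by a factor of 1.41. This rests on the plan's own Wald formula, equal allocation, and adherence being measurable only in the SPARC arm. With Wilson intervals at 0.70 the comparison is 0.169 against 0.123, about 37% wider, so the conclusion does not depend on the method.

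The stated range is correct for retention. The fault lies in the planning statement: the intervals reported under 14.2 will have their true width if the right denominator is used, nothing is biased, and the sample size need not change. The missing precision for the usability proportions is an omission of the same kind. Its n = 25 is inferred from who receives the app, and is less certain for TSUQ, which the plan describes as a patient and provider scale.

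**What to change.** Restate the precision in 14.1 by outcome, each with its denominator:

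- **Retention:** n = 50, ±0.11 at 0.80.
- **Recruitment:** number approached, about 63 if 80% agree, ±0.10.
- **Proportion adherent:** n = 25, ±0.12 to ±0.18 if drop-outs count as non-adherent. If they are excluded, down to n = 20 and ±0.13 to ±0.20. State which.
- **Proportions above average on SUS, uMARS and TSUQ:** ±0.17 at n = 25 and ±0.19 at n = 20, with a statement of who completes each scale.

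Say whether the .70 benchmark is a share of subjects or a mean session rate. If a share, define when a subject counts as adherent; if a mean rate, replace the proportion precision with one based on an SD at n = 25. Name the interval method and use it for both planning and reporting. The figures above are Wald, to match the plan; Wilson or exact intervals are preferable at n = 20 to 25, and the planning figures should then be recomputed to match.

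The cost is a few sentences and recalculated figures. No patients, data or analyses are added. The only drawback is a less favourable stated precision for adherence.

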#### 9.1.1 Synopsis of Our Research Pertinent to the Study

**Mobile phone & mHealth Attitudes Survey:** Out of 194 SPs with SAF (mean age 47 yrs, 65% AAs), 98% owned a cell phone and 84% owned a smart phone with internet activation. They were facile in use of cell phones (e.g., 98% sent/received SMS, 36% browsed internet, 34% sent/received email, 42% downloaded apps). SPs reported high acceptability of using apps to manage their stress & fatigue. Following a video demo of the TT app (Fig. 1a,1b) and a Fitbit Walking app, all SPs with “significant” SAF (Fatigue Assessment Scale (FAS) score  $\geq 22$ ) either “agreed” or “strongly agreed” both apps would help them manage stress and fatigue and would be willing to use the apps as directed if they were free. SPs liked the overall design and ease of use of the TT app over the Fitbit walking app (4.1 vs 3.9 on 5-point scale).

**Associations between stress, fatigue and self-efficacy for coping with SAF.** The mean FAS score was 31.0, with “significant” fatigue defined as a score  $\geq 22$ . Using the Perceived Stress Scale (PSS-4), 50% reported significant stress, defined as a score of  $\geq 8$ . Similar results were reported by Cox et. al., who found 55% of SPs reported PSS-4 scores  $\geq 8$ . Fatigue levels (FAS score) were moderately correlated ( $r=0.65$ ) with perceived stress levels. We also assessed fatigue self-efficacy in coping with SAF. We relabeled the 8 item Likert-type Multiple Sclerosis[MS]-Fatigue Self-Efficacy Scale (FSE, internal consistency: Cronbach  $\alpha$  0.89-0.94). SPs confirmed its applicability to SAF, no comprehension issues were identified, and Cronbach  $\alpha$  was .97. Mean scores/standard deviations on the FSE indicated low self-efficacy in coping with SAF (e.g., mean scores SPs: 47.3 vs MS data: 46.8; range 0-100 with 100 representing

SPARC

high FSE). FSE scores were highly correlated to both PSS (-0.89) and FAS (-0.97) scores.

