**SPARC proof of concept trial:** Based upon our survey responses indicating overall slightly higher preference for the the SPARC prototype app over the Fitbit app in its design, ease of use & self-efficacy of using if free service assistance provided, a 3 mth. proof of concept trial was conducted with SPs with SAF (n=18). The SPARC group engaged in 10 min sessions twice per day and the other group received standard of care (SC). We observed high acceptability (100% participation: 5.5% attrition), self- efficacy for following the SPARC regimen (mean 4.6 on 5-point Likert scale) and adherence over the 3 months (.mo1:81%, mo2:72%, mo3:65%-1 subject began chemotherapy during mth3). As shown in Fig1a&b, the SPARC group reported greater reductions in stress (PSS) and fatigue (FAS) compared to the SC group at months 1 & 3 (all ps <.05- .07). We received helpful suggestions from the participants for further adapting the SPARC app for SPs (e.g., video module having a SP engaging in BAM, several video testimonials by SPs stating how it helps increase energy levels, reduces stress, fatigue and improves quality of sleep; MD give overview of sarcoidosis & role of stress & fatigue).

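### The SDs of 0.5 to 2.0 behind the stated precision for usability scores do not match SUS, uMARS and TSUQ as the benchmarks score them (>68, >64, >60)

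*Combined protocol and SAP*

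**What the plan says.** Section 14.1 sets the sample size on pragmatic grounds and then describes the precision it gives. It lists SUS, TSUQ and uMARS as usability measures, beside frequency and duration of app use. For the continuous ones its statement opens: "For continuous usability measures, 95% confidence intervals (CIs) can be estimated with precisions ranging from". The half-widths it then gives start at ±0.20 and end at ±0.78, and it describes them as "corresponding to estimated standard deviations (SDs) ranging from 0.5 to 2.0, respectively". Section 14.2 keeps the three surveys in the continuous group and plans medians and means with 95% intervals for them.

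The synopsis and sections 7, 8 and 9.1.3 set the usability benchmark on the same surveys. In section 9.1.3, at least 75% "of sample will score above average on SUS(>68), uMARS (>64), TSUQ (>60").

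For the secondary measures, section 14.1 uses one SD range for change in PSS, FAS, QoL, FSE and TSRQ together. Within-group precision is ±1.5 to ±2.4 (the lower figure is misprinted and is read here as 1.5), "corresponding to estimated SD of change scores ranging from 3.7 to 6.1, respectively". Between-group precision is ±2.8 to ±3.7, "for SDs of differences in scores from 5.0 to 6.7 SD units". Section 9.1.1 describes FSE as "range 0-100 with 100 representing" high self-efficacy. Table 2 gives FAS and PSS ten items each.

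Neither SD range has a stated source. No SD for SUS, uMARS, TSUQ or FSE is printed anywhere in the document.

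**The concern.** A precision statement is useful only if its SD belongs to the score that will be reported. Cut-offs of 60 to 68 mean that the surveys are scored in tens of points. SDs of 0.5 to 2.0 look like those of a single rating on a short scale. If the surveys were instead analysed as averages of 5-point items, no user could pass a cut-off of 60. The benchmarks and the precision statement therefore cannot both refer to one such scoring.

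Section 14.1 puts the trial's weight on feasibility and usability rather than hypothesis testing, so these half-widths are its only quantitative account of how well the mean survey scores will be known. A reader who relies on ±0.78 would expect mean scores far more sharply estimated than 25 users are likely to give. A similar question arises for FSE, which shares one change-SD range with two ten-item scales although it runs to 100.

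**Working it through.** **Inputs.** From section 14.1: 50 patients, 25 per group; 95% intervals; SDs of 0.5 to 2.0 (usability), 3.7 to 6.1 (within-group change) and 5.0 to 6.7 (between-group difference). From section 9.1.3: cut-offs >68, >64 and >60. From section 9.1.1: FSE range 0-100. All SDs in steps 3 and 4 other than 6.1 are assumptions.

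**1. Reproduce the plan's figures.** Half-width of one mean = 1.96 × SD / √n; of a difference = 1.96 × SD × √(2/n); n = 25.

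- Usability: 1.96 × 0.5 / 5 = 0.196; 1.96 × 2.0 / 5 = 0.784. Stated: 0.20 and 0.78.
- Within-group change: 1.96 × 3.7 / 5 = 1.45; 1.96 × 6.1 / 5 = 2.39. Stated: 1.5 and 2.4.
- Between groups: 1.96 × 5.0 × √(2/25) = 2.77; 1.96 × 6.7 × √(2/25) = 3.71. Stated: 2.8 and 3.7.

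All agree. With n = 50 the usability figures would be 0.14 and 0.55, so the plan used 25. With t instead of z they would be 0.21 and 0.83, so it used the normal quantile.

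**2. Check the usability SDs against the scoring.** Under normality, an SD of 2.0 puts 95% of users within 1.96 × 2.0 = 3.9 points of the mean, and an SD of 0.5 within about 1 point. That is implausibly tight for surveys with cut-offs of 60 to 68. By contrast, the largest possible SD on a 1-to-5 item is (5 − 1)/2 = 2.0, so the range 0.5 to 2.0 would fit such an item.

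**3. Precision on the scoring of the cut-offs, n = 25.**

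| Assumed SD (points) | Half-width | Relative to 0.784 |
|---|---|---|
| 5 | 1.96 × 5 / 5 = ±1.96 | 2.5 times |
| 10 | 1.96 × 10 / 5 = ±3.92 | 5 times |
| 20 | 1.96 × 20 / 5 = ±7.84 | 10 times |

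With 20 users, which a 20% drop-out would leave, SDs of 10 and 20 give ±4.4 and ±8.8. To reach ±0.78 with an SD of 10 would take (1.96 × 10 / 0.78)², about 630 users.

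**4. FSE.** With equal SDs at baseline and follow-up, SD of change² = 2 × SD² × (1 − r), so r = 1 − 6.1² / (2 × SD²) = 1 − 37.21 / (2 × SD²).

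| Assumed baseline SD | Pre-post correlation needed for a change SD of 6.1 |
|---|---|
| 10 | 0.81 |
| 15 | 0.92 |
| 20 | 0.95 |
| 25 | 0.97 |

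The upper end of the plan's range is possible for FSE if baseline scores vary little. It becomes demanding as the baseline SD rises. If the change SD were 10 to 20, the half-widths would be ±3.9 to ±7.8 within group and ±5.5 to ±11.1 between groups (1.96 × SD × √(2/25)).

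**The case against.** The plan states its precision conditionally on given SDs, and every half-width follows from its SD. A reader might infer a calculation error; there is none.

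A reader might also infer that the primary benchmark is compromised, or that a mean near 68 would be wrongly judged to have passed. The documents do not support this. The cut-offs classify individual users, the benchmark is the share above them, and no mean is compared with a cut-off. The precision of that share comes from the separate statement on proportions in section 14.1. No test, sample size or go/no-go rule depends on the SDs questioned here.

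The range 0.5 to 2.0 also covers frequency and duration of use, where it may fit. The group's earlier 5-point ratings, such as "mean 4.6 on 5-point Likert scale" in section 9.1.1, show that it has used such scales, but that rating concerned confidence in following the regimen. Nothing links it to the SDs in section 14.1.

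The range 3.7 to 6.1 is plausible for totals of the ten-item FAS and PSS and is not shown wrong for them. A 0-100 range does not by itself fix the SD of change, so it would go too far to say that FSE intervals will be wider than stated. Estimating variability of the secondary outcomes is also one of the trial's aims.

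All of this stands. It leaves open why the three surveys are covered by SDs that do not suit their scoring, since the text does not restrict the range to the usage measures.

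**Conclusion.** The point holds for SUS, uMARS and TSUQ. The stated ±0.20 to ±0.78 does not describe these surveys on the scoring that their cut-offs imply. The true size cannot be derived from the documents, because they give no SD for the totals. Even an assumed SD of 5 points gives 2.5 times the stated maximum, and 10 to 20 points gives 5 to 10 times. These figures assume that all 25 SPARC users answer at week 12.

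For FSE the pooled change-SD range is doubtful but not shown to be wrong; the answer depends on an unstated baseline SD and pre-post correlation. The consequence is moderate: the expected precision of descriptive means is overstated, while the 75% benchmark and the choice of 50 patients are untouched.

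**What to change.** In section 14.1:

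- State for SUS, uMARS and TSUQ the score to be analysed and its range, matching the cut-offs. Give an assumed SD with its source for each, and restate the half-width. For example, assumed SDs of 10 to 20 points with 25 users give ±3.9 to ±7.8; these SDs are placeholders until sourced values replace them.
- Keep the SD range of 0.5 to 2.0 only for usability measures on a scale where it fits, and name them.
- Give FSE its own assumed SD of change, with source, and its own within-group and between-group precision. Name the instruments to which 3.7 to 6.1 applies.

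This is a rewording of one section. Patients, visits, sample size and benchmarks do not change. The only cost is that the stated precision becomes less favourable.
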